# Effects of vitamin C administration on extravascular lung water in patients with severe features of preeclampsia: a randomized, placebo-controlled trial

#### **RATIONALE**

Risk of fluid over-resuscitation is high in preeclampsia due to endothelial dysfunction and resulting increased vascular permeability (1). The Confidential Enquiry into Maternal Deaths in the UK reported six maternal deaths between 1994 and 1996 due to adult respiratory distress syndrome (ARDS) that appeared to be related to poor fluid management in women with preeclampsia (2). On the basis of these reported deaths, recommendations on limiting intravenous fluids to not more than to 80 ml/hour (or 1 ml/kg/h) have been made (3). Nevertheless, preeclampsia remains the leading cause of pulmonary edema in the peripartum period (4). Moreover, in some preeclamptic patients higher rates of intravenous fluid administration may be necessary to adequately correct tissue hypoperfusion.

Zieleskiewicz et al. were the first to demonstrate that lung ultrasound (LUS) can be used to objectively evaluate increased extravascular lung water (EVLW) in patients with preeclampsia (5). Ambrozic et al. recently confirmed these results and showed that the amount of EVLW assessed by LUS is increased in preeclamptic patients compared to healthy controls and that it decreases rapidly in the first four days following delivery (6).

It has been reported that administration of high-dose ascorbic acid (vitamin C) reduces vascular permeability in animals (7-9). In 2000, Tanaka et al. reported an RCT involving 37 patients with major burns (>30% body surface area) randomized regarding whether or not to receive an infusion of IV vitamin C, 66 mg/kg/h for the first 24 hours of hospitalization. Patients in the vitamin C group required less fluid resuscitation, had higher urine output, and developed less wound edema. This translated into improved oxygenation and less time on mechanical ventilation among the vitamin C group (average of 12 vs. 21 days of ventilation, p=0.03) (10). In 2002, Nathens et al. randomized patients shortly after admission to a surgical ICU to no therapy vs. a combination of enteral vitamin E plus IV vitamin C 1000 mg/8h until ICU discharge. The primary endpoint was a composite of pneumonia or ARDS. Although there were trends towards fewer pulmonary complications among patients treated with antioxidants, these did not reach statistical significance (the study was underpowered due to low rates of respiratory complications). However, patients treated with vitamins E and C

fared better on a variety of secondary endpoints including less time on the ventilator and less multiorgan failure (11).

In women with established preeclampsia, there is evidence of oxidative stress and decreased concentrations of vitamin C (12). An initial RCT on prophylactic supplementation with oral antioxidants, including 1g vitamin C daily, showed a significant reduction in preeclampsia (8 percent vs. 17 percent) in high-risk pregnancies (13). Subsequent large RCTs have, however, reported no significant reduction in the risks of preeclampsia, intrauterine growth restriction, or the risk of death or other serious outcomes in infants associated with oral vitamin C supplementation (14,15). There are no studies to date on use of higher dose IV vitamin C administration for reduction of capillary leak and consequently EVLW in patients with severe forms of preeclampsia. Given the safety (see below) and low costs of vitamin C this could be a promising approach to increase fluid tolerance in these patients. If vitamin C reduces vascular permeability in preeclampsia patients to the same degree that it seems to reduce vascular permeability in other conditions, such as burns, it could reduce the risk of pulmonary complications associated with this disease. At the same time, vitamin C therapy could allow safe additional fluid administration in patients with preeclampsia who are fluid responsive and in whom further increases in preload would be beneficial for preventing end-organ damage such as pre-renal acute kidney injury.

## Safety of vitamin C

Safety of vitamin C has been well established even at high doses. For example, none of the above studies reported any adverse event, despite the use of very high doses by Tanaka et al. (1.6 grams/kg over 24 hours) (10). One potential concern regarding vitamin C is that it may be metabolized into oxalic acid, leading to calcium oxalate nephropathy. This doesn't seem to be a significant problem for several reasons:

- Oxalate formation is a dose-dependent toxicity. This has rarely been reported from short courses of IV vitamin C, but only at much higher doses (>40 grams/day) (16).
- In 2014, Fowler et al. published a phase I safety trial of vitamin C in patients with severe sepsis. Their prospective RCT involved patients with severe sepsis in a medical ICU. 24 patients were randomized to receive placebo, low-dose vitamin C (12.5 mg/kg IV/6hr), or high-dose vitamin C (50 mg/kg IV/6hr). The primary endpoint was safety and tolerability, with no adverse events noted (17).

• Recently Marik et al. published a before-after study investigating the impact of treating sepsis with a combination of thiamine 200 mg IV/12hr, Vitamin C 1.5 g/6hr, and hydrocortisone 50 mg IV/6hr. Mortality was substantially reduced in patients receiving vitamin C (*p*<0.001). Moreover, vitamin C use correlated with *improved* renal outcomes (the rate of dialysis was reduced from 33% to 10%, *p*=0.02) (18).

Another concern which has been raised is that vitamin C at extremely high doses may have a pro-oxidant effect. This was shown not to occur even at a dose of 7.5 grams IV daily (19).

#### **OBJECTIVE**

The objective of the study is to determine whether administration of vitamin C (1.5g/6 hours) in the first three days post-partum reduces the amount of EVLW assessed by LUS in patients with preeclampsia with severe features.

#### **INCLUSION CRITERIA**

Consecutively admitted patients with singleton pregnancies complicated by preeclampsia with severe features will be included in the study at hospital admission. Severe features of preeclampsia will be defined using the American College of Obstetricians and Gynecologist Task Force on Hypertension in Pregnancy recommendations (table) (20).

Inclusion criteria: Singleton pregnancy with severe featutes of preeclampsia (any of the following)

- Systolic blood pressure of 160 mm Hg or higher, or diastolic blood pressure of 110 mm Hg or higher on two occasions at least 4 hours apart while the patient is on bed rest (unless antihypertensive therapy is initiated before this time)
- Thrombocytopenia (platelet count less than  $100 \times 10^9 / L$ )
- Impaired liver function as indicated by abnormally elevated blood concentrations of liver enzymes (to twice normal concentration), severe persistent right upper quadrant or epigastric pain unresponsive to medication and not accounted for by alternative diagnoses, or both
- Progressive renal insufficiency (serum creatinine concentration greater 97 μmol/L or a doubling of the serum creatinine concentration in the absence of other renal disease)

- Pulmonary edema
- New-onset cerebral or visual disturbances

#### STUDY PROTOCOL

All patients will be managed in a high dependency setting. Fluid intake and urine output will be assessed hourly. Intravenous fluids will be limited to 80 ml/h, and neither additional fluids nor diuretics will be routinely administered.

After written informed consent, patients will be randomized into two groups. They will receive either 1,5g of IV vitamin C in 100 ml 0.9% NaCl within 30 min of delivery and then every 6 hours for the first 72 hours post-partum or placebo (100 ml of IV 0.9% NaCl within 30 min of delivery and then every 6 hours for the first 72 hours post-partum) (Figure).

Randomization will be performed in a 1:1 ratio using a computer generated randomization sequence. The randomization codes will be kept at the pharmacy department as will be the preparations (vitamin C and normal saline). Physicians and patients will be blinded to the type of medication administered by nurses who will prepare and administer the study medications.

[figure not shown]

Figure: Time line of the study; LUS lung ultrasound; ECS Echo Comet Score

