#### STUDY OUTCOME

The primary outcome studied will be the Echo Comet Score (ECS) at days 1, 2, and 3 following delivery in the vitamin C vs. placebo group. Mann Whitney U-test will be used for comparing ECS between the two study groups (vitamin C vs. placebo)

Lung ultrasound assessment will be performed once daily in the first three days following delivery. The amount of EVLW will be determined by the ECS obtained by summing the number of B-lines or "comet tails" found on each of the 28 chest wall areas. In addition to the 28 region technique, the ECS using the more clinically applicable 8 anterior region technique will also be documented.

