#### SAMPLE SIZE CALCULATIONS

Sample size was calculated using data from Tanaka et al., who showed a reduction in fluid volume requirements in burn patients (a marker of vascular permeability) of 46% (5.5 ml/kg vs. 3.0 ml/kg indexed by burn size) associated with vitamin C treatment (10). We have recently found an average ECS on the first day following delivery of 13 (with a standard deviation of  $\pm$  7) in patients with severe features of preeclampsia not treated with vitamin C (6). To discern a decrease of 46% in ECS between the study (vitamin C) and placebo groups we would require a minimum sample size of 17 patients per group, which was calculated using a desired power of 0.80 and an alpha of 0.05.

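### Could nurses who are not listed as blinded, together with an unclear 80 ml/h limit, make total IV fluid differ between the arms?

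*Combined protocol and SAP*

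**What the plan says.** Four statements under STUDY PROTOCOL and one under STUDY OUTCOME bear on this point.

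- Fluid limit: "Intravenous fluids will be limited to 80 ml/h, and neither additional fluids nor diuretics will be routinely administered".
- Study infusions: the active arm receives "1,5g of IV vitamin C in 100 ml 0.9% NaCl within 30 min of delivery and then every 6 hours for the first 72 hours" after delivery; the placebo arm receives "100 ml of IV 0.9% NaCl within 30 min of delivery and then every 6 hours for the first 72 hours post-partum". Volume, diluent and timing are the same.
- Blinding: "Physicians and patients will be blinded to the type of medication administered by nurses who will prepare and administer the study medications". The randomization codes and both preparations are held in the pharmacy department.
- Monitoring: "Fluid intake and urine output will be assessed hourly".
- Analysis: "Mann Whitney U-test will be used for comparing ECS between the two study groups". No summary of fluid intake or balance by arm is listed.

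The readable text does not say whether the study infusion counts toward the hourly limit. The figure with the study time line is not reproduced in the text available here, so the absence of an infusion duration cannot be held against the plan.

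**The concern.** Randomization balances the arms at allocation, not the care that follows. If staff who know the arm can influence other treatment, that treatment may drift apart. Fluid is the obvious candidate here, because the RATIONALE says "Risk of fluid over-resuscitation is high in preeclampsia due to endothelial dysfunction and resulting increased vascular permeability" and the outcome is a measure of lung water.

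Three features seem to combine. The nurses who make up the infusion presumably know what is in it. The limit can be read two ways. Fluid below the limit, and fluids or diuretics that are not routine, are left to judgement. If the two readings came to be used differently in the two arms, an ECS difference due to fluid could be taken for a vitamin C effect, or could mask one, and the planned test could not tell them apart.

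**Working it through.** The plan gives no figure for total fluid, so there is none to reproduce. The check asks how large a difference between arms the text allows.

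**Inputs.** Limit 80 ml/h; study bag 100 ml every 6 h for 72 h in both arms (STUDY PROTOCOL). ECS mean 13, SD 7, target fall 46%, 17 per group (SAMPLE SIZE CALCULATIONS).

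**Step 1, size of the bag.** 100/6 = 16.7 ml/h on average, which is 16.7/80 = 20.8% of the limit. Per day, 4 × 100 = 400 ml, against 80 × 24 = 1,920 ml. Over 72 h it is 1,200 ml with 12 doses, or 1,300 ml if a 13th is given at hour 72, against 80 × 72 = 5,760 ml.

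**Step 2, the two readings, with other fluid run up to the limit.**

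| Reading | Vitamin C | Placebo | Difference |
|---|---|---|---|
| Bag inside the limit | 80 ml/h (63.3 other + 16.7 bag) | 80 ml/h | 0 |
| Bag on top of the limit | 80 + 16.7 = 96.7 ml/h | 96.7 ml/h | 0 |

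The ambiguity changes the regimen delivered in both arms. By itself it does not change the contrast between them.

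**Step 3, what a difference would need.** Let p be the share of women in an arm whose bag is given on top of the limit. Mean total fluid at the limit is 80 + 16.7p, so the difference between arms is 16.7 × (p in one arm − p in the other). Inconsistent practice unrelated to arm makes the two shares equal in expectation, so the expected difference is 0. The full 16.7 ml/h (400 ml/day, 1.2 to 1.3 L by 72 h) appears only when one share is 1 and the other 0, with other fluid at the limit throughout.

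**Step 4, from fluid to ECS.** The documents give no ECS change per millilitre, so any shift is an assumption. The standard error of a difference in means is 7 × √(2/17) = 2.40. An assumed shift b gives a two-sided 5% test a false-positive rate of 1 − Φ(1.96 − b/2.40) + Φ(−1.96 − b/2.40). For b = 1, 2 and 3 points this is 7.0%, 13.2% and 23.9%. These rates would follow from a bias of that size from any source. They do not show that this source produces one. The largest, 3 points, is half of the whole hypothesised effect (0.46 × 13 = 5.98; 3/5.98 = 50%).

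**The case for a change.** The strongest case for a change is that the three textual gaps are real, fluid is the co-treatment most likely to move ECS, and the remedy looks small: a sentence on how the bag relates to the limit, bags made up in the pharmacy that already holds codes and products, and a table from data already collected. The documents do not say who orders other fluid, so blinded physicians cannot be assumed to control it.

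The gaps stand. The inference from them to a fluid difference does not.

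- It might be argued that a nurse would count the placebo bag as IV fluid and the active bag as a drug. Both are 100 ml of the same saline, so their content gives no reason to count them differently.
- A bias needs several undocumented steps together: nurses rather than blinded physicians setting other fluid, counting equal volumes differently by arm, doing so consistently, and running other fluid near the limit.
- The limit and the infusion schedule do not contradict each other. One is a general rule and the other a study procedure; what is missing is a clarification of clinical practice, which is for the investigators.
- Pharmacy preparation is not plainly cheap. It means 12 to 13 bags per woman around the clock, the first due within half an hour of a delivery whose time cannot be scheduled. The documents do not show that the pharmacy can do this. Nurse preparation with physicians and patients blinded is a fair operational trade-off.
- A fluid table by arm would be useful to readers, but it is descriptive and alters no planned result. The hourly record lets analysts produce it without a protocol change.

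**Conclusion.** No change to the plan follows. The text leaves nurses off the blinded list, does not say how the study bag relates to the 80 ml/h limit, and plans no fluid summary by arm. Under either reading, applied alike to both arms, the resulting fluid difference is 0 ml. The 16.7 ml/h bound is correct arithmetic, but it describes complete, arm-specific divergence at the maximum rate, for which the documents give no evidence. The error rates in Step 4 rest on assumed ECS shifts that nothing in the documents ties to fluid volume, so they carry no weight here.

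The conclusion rests on two assumptions: that the limit is applied the same way in both arms, and that other fluids and diuretics are managed without regard to arm. Neither is guaranteed by the text. Both can be examined afterwards, because intake and urine output are assessed hourly. Sample size, alpha and the planned test are unaffected.

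### Do the nurses' knowledge of allocation and the unnamed ultrasound operator undermine the blinded reading of the Echo Comet Score?

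*Combined protocol and SAP*

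**What the plan says.** The only statement on blinding is under STUDY PROTOCOL: "Physicians and patients will be blinded to the type of medication administered by nurses who will prepare and administer the study medications". The sentence before it places the codes and the products with the pharmacy: "The randomization codes will be kept at the pharmacy department as will be the preparations (vitamin C and normal saline". The arms are 1.5 g vitamin C in 100 ml of 0.9% saline or 100 ml of saline alone, started within 30 minutes of delivery and repeated every 6 hours for 72 hours. Intravenous fluid is limited to 80 ml/h for all patients, "Fluid intake and urine output will be assessed hourly", and "neither additional fluids nor diuretics will be routinely administered".

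STUDY OUTCOME makes the Echo Comet Score (ECS) on days 1, 2 and 3 the primary outcome. It is "obtained by summing the number of B-lines" over 28 chest wall areas. On the conduct of the scan it says: "Lung ultrasound assessment will be performed once daily in the first three days following delivery". No operator is named, and the reader's blinding is not mentioned separately.

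**The concern.** Two features together look like a weakness. First, whoever makes up the infusion sees whether vitamin C goes into the bag, and that nurse also gives it. No coded infusion is described, and no separation of preparation from bedside care. Staff who probably know the arm are therefore near the patient throughout the 72 hours of dosing, the period in which the scans are done.

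Second, a B-line count depends on judgement, and the plan does not identify the person making it. If that person learned the arm, counts could drift in the expected direction. Knowledge of the arm could also affect extra fluids or diuretics, which are excluded only as routine treatment, and no table of these by arm is planned. At stake would be whether a difference in ECS could be credited to vitamin C.

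**Working it through.** **Inputs.** From SAMPLE SIZE CALCULATIONS: "We have recently found an average ECS on the first day following delivery of 13", SD 7; "To discern a decrease of 46% in ECS between the study (vitamin C) and placebo groups"; power 0.80; alpha 0.05; 17 per group. From STUDY OUTCOME: 28 areas, three daily scans. From STUDY PROTOCOL: a dose every 6 hours for 72 hours.

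**1. The plan's own figure.** The difference is 0.46 × 13 = 5.98. With n = 2(z_α + z_β)²(SD/difference)² and one-sided alpha 0.05, 2 × (1.645 + 0.842)² × (7/5.98)² = 16.9, so 17 per group: the plan's figure. With two-sided alpha the same formula gives 22. Sidedness is a separate matter and has no bearing on blinding. The total is 34 women.

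**2. How large a reading error would matter.**
- Planned effect in SD units: 5.98/7 = 0.85.
- Treated mean: 13 − 5.98 = 7.02.
- Per chest area: 13/28 = 0.46 against 7.02/28 = 0.25, a difference of 0.21, or one B-line in every 28/5.98 = 4.7 areas.
- In proportion: 0.214/0.464 = 46%.

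The figure of 0.21 sounds tiny, but it is the planned effect divided by 28. To produce that effect from nothing, a reader would have to miss 46% of B-lines in one arm and none in the other. The 28 × 3 = 84 area readings per woman describe workload, not bias. The mean of 13 applies to day 1 only.

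Smaller errors would still count. Suppose, purely as an assumption, that there is no true effect and the reader shifts the difference between arms by b points. The standard error is 7 × √(2/17) = 2.40. The chance of a significant result favouring vitamin C at two-sided 0.05 is about Φ(b/2.40 − 1.96), by normal approximation:

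| Assumed b | Chance |
|---|---|
| 0 | 2.5% |
| 1 | 6% |
| 2 | 13% |
| 3 | 24% |

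So a partial reader could mislead this trial. The table does not show that the plan supplies one; none of these values of b comes from the documents.

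**3. Is there a route from the nurse to the score?** Knowledge of the arm must reach the reader or change co-treatment.
- *Reader.* The blinding sentence covers physicians as a class, with no exception for the one who scans. No passage says that a nurse, or anyone else who knows the arm, reads the scans.
- *Co-treatment.* Volume and schedule are the same in both arms, the fluid limit is common, and extra fluids and diuretics are not routine. Non-routine use remains possible, but nothing says that nurses decide it; if physicians order it, they are blinded.
- *Preparation.* The pharmacy sentence is ambiguous about the form in which products are supplied. That nurses know the arm is a fair inference from their preparing the dose, but it is not stated.

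**4. Cost of closing the nurse gap.** 72/6 = 12 doses per woman, or 13 if one is also given at hour 72. For 34 women this is 12 × 34 = 408 to 13 × 34 = 442 doses, day and night. Each would need someone not caring for that patient to prepare it. If that is another nurse on duty, a nurse on the unit still knows the arm.

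**The case for a change.** The strongest case for a change is that blinding cannot be restored once the scans have been read, that the outcome is a judgement-based count with no second reading described, and that one sentence would settle who reads it. A preparer who knows the arm is ordinary; one who is also the bedside nurse, with no stated barrier to the patient or the reader, is less so. Nor can a review of a protocol be expected to demonstrate bias that has yet to occur.

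Much of this is fair. The operator is indeed not named. If a sonographer or nurse did the scan, the blinding sentence would not cover that person, so naming the operator and confirming that they are blinded, take no part in preparing or giving the drug and cannot see the preparation record would be a sensible clarification. Coded infusions made up away from the bedside would be a further strengthening where local workflow already allows it. But this is detail that a site following the plan would ordinarily fill in the same way. A table of fluids, urine output and diuretics by arm is a reporting preference and can be produced for whatever is recorded.

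**Conclusion.** No change to the plan is needed. The missing operator is a gap that the existing blinding of physicians fills if a physician scans. The nurse's role is an openly stated practical trade-off: doses begin within 30 minutes of an unscheduled delivery and continue round the clock, and separate preparation of some 408 to 442 doses is not clearly cheap and need not remove knowledge of the arm from the ward.

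The documents give no size or direction for any bias, and none is estimated here. The 0.21 B-lines per area is the planned effect of 5.98 points (0.85 SD) on another scale, not evidence of a fault.

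The conclusion assumes that a physician, or someone else kept unaware of the arm, performs the scan, and that physicians order any non-routine fluids or diuretics. The documents state neither outright. If a nurse who prepares the drug also counted B-lines, the concern would be real; nothing in the text suggests it.

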#### STUDY OUTCOME

The primary outcome studied will be the Echo Comet Score (ECS) at days 1, 2, and 3 following delivery in the vitamin C vs. placebo group. Mann Whitney U-test will be used for comparing ECS between the two study groups (vitamin C vs. placebo)

Lung ultrasound assessment will be performed once daily in the first three days following delivery. The amount of EVLW will be determined by the ECS obtained by summing the number of B-lines or "comet tails" found on each of the 28 chest wall areas. In addition to the 28 region technique, the ECS using the more clinically applicable 8 anterior region technique will also be documented.

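### Three primary days and no rule for success: the 5% error rate is not secured, and is about 8.5–14% if any one significant day counts

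*Combined protocol and SAP*

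**What the plan says.** The STUDY OUTCOME section of the combined protocol and SAP sets the endpoint: "The primary outcome studied will be the Echo Comet Score (ECS) at days 1, 2, and 3 following delivery". Scans are daily: "Lung ultrasound assessment will be performed once daily in the first three days following delivery". The only analysis named is a Mann-Whitney U-test of ECS between vitamin C and placebo. No section names a key day, a summary over days, a testing order, a multiplicity adjustment or a criterion for success.

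The SAMPLE SIZE CALCULATIONS section plans a single comparison. Its control value comes from one day: "We have recently found an average ECS on the first day following delivery of 13", with a standard deviation of 7. The result is 17 per group, "which was calculated using a desired power of 0.80 and an alpha of 0.05". That alpha is not divided between days, and the section does not declare day 1 to be the primary time point.

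The OBJECTIVE covers the whole period, asking whether vitamin C "in the first three days post-partum reduces the amount of EVLW assessed by LUS". The RATIONALE says of extravascular lung water that "it decreases rapidly in the first four days following delivery".

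**The concern.** A Mann-Whitney test takes one value per patient, and the primary outcome supplies three. The protocol does not say how the two fit together. The natural reading, which is an inference, is a separate test on each day at 0.05.

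Three primary p-values without a success rule let the rule be chosen after the results are seen. A chance finding on one day could be reported as a positive trial. Equally, a real day-1 effect could be called negative because day 3 missed. Discordant days are plausible: lung water is expected to fall quickly after delivery, so the day-1 mean and SD need not hold on days 2 and 3. With 34 women in total, such disagreement would be hard to interpret afterwards.

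**Working it through.** **Inputs.** From SAMPLE SIZE CALCULATIONS: control mean 13, SD 7, reduction 46%, power 0.80, alpha 0.05 (sidedness not stated), 17 per group. From STUDY OUTCOME: three days, Mann-Whitney test. Assumed, because the documents give none: between-day correlation from 0 to 0.9, equal for every pair of days.

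**1. The plan's own figure.** Difference = 0.46 × 13 = 5.98 points; standardised, 5.98 / 7 = 0.854. With n per group = 2(z_α + z_β)² / 0.854²:

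- one-sided 0.05: 2 × (1.645 + 0.842)² / 0.730 = 16.9, which rounds up to 17
- two-sided 0.05: 2 × (1.960 + 0.842)² / 0.730 = 21.5, which rounds up to 22

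The stated 17 is therefore one comparison on day-1 inputs, and it reproduces only as a one-sided calculation. Sidedness is a separate issue; it appears here only because it explains why the two-sided powers below fall short of 0.80.

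**2. Any-day rule, independent days.** 1 − 0.95³ = 0.143.

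**3. Correlated days.** The any-day error is 1 − P(all three |Z| ≤ 1.96), and the all-days error is P(all three |Z| > 1.96), for a trivariate normal Z. This was checked by simulating two-sided Mann-Whitney tests with 17 per group (40,000 trials per setting, normal scores).

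| Correlation | Any day, trivariate normal | Any day, Mann-Whitney | All days, trivariate normal |
|---|---|---|---|
| 0 | 14.3% | 13.9% | 0.01% |
| 0.3 | 13.6% | 13.3% | 0.08% |
| 0.5 | 12.6% | 12.3% | 0.3% |
| 0.7 | 11.0% | 11.1% | 0.9% |
| 0.9 | 8.4% | 8.6% | 2.3% |

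A correlation that decays with time between scans (first-order autoregressive) gives 8.8% at 0.9. One-sided Mann-Whitney tests give 14.0% down to 8.2%, so the inflation does not depend on sidedness. The simulated all-days error is 0.02% to 2.0%. Day 1 alone rejects in 4.7–5.0% of null trials.

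**4. Power under each rule** (Mann-Whitney, 17 per group, two-sided; ranges are for correlations 0.5 to 0.9).

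| Effect on days 1/2/3, as % of 0.854 SD | Day 1 alone | All three days | Three-day mean |
|---|---|---|---|
| 100/100/100 | 0.65 | 0.40 to 0.54 | 0.82 to 0.68 |
| 100/75/50 (assumed) | 0.65 | 0.13 to 0.21 | 0.58 to 0.45 |
| 50/75/100 (assumed) | 0.21 | not computed | 0.58 to 0.44 |

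**5. Error of the proposed replacements.** Under no effect, day 1 alone rejects as in step 3, and the three-day mean rejects in 4.9–5.0%.

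**The case against.** The strongest reply is that the protocol never says a single day is enough. The inflated figure belongs to one possible rule; under a day-1 rule or an all-days rule the error is at or below 5%. This stands: what is established is a missing success rule, and 8.5–14% is what follows if the gap is filled in the most permissive way.

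A second reply is that the sample size section points to day 1, with days 2 and 3 as its time course. That is a fair reading and supports making day 1 the default repair. It is not a declaration, however. The outcome section lists three days on equal terms and the objective spans all three.

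Three further points qualify the numbers:

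- Zero correlation between consecutive days in the same woman is unlikely. At 0.5 to 0.9 the any-day error is about 8.5–12.5%, though that narrower range is also an assumption.
- With two-sided tests, the totals count false findings in both directions. False claims of benefit are about half, 4.3–7.1% against a nominal 2.5%, so the relative inflation is the same.
- The power figures assume normal scores and equal SDs on all days, and the fading and growing effect patterns are invented for illustration. The null error rates are much less sensitive to these choices.

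**Conclusion.** The concern holds. As written, the plan yields three unadjusted primary p-values and no rule for turning them into one conclusion. Depending on the rule adopted later, the trial-wide false-positive rate at 17 per group runs from almost zero (all days), through about 5% (day 1 only), to about 8.5–14% (any day, assumed correlations 0.9 down to 0). The all-days reading controls error but brings power below the 0.65 of day 1 alone, even when the effect is constant.

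This must be fixed, because it decides how the trial's only primary question is answered and cannot credibly be repaired after unblinding.

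**What to change.** Before unblinding, specify one primary test at 0.05 in the STUDY OUTCOME section and state its sidedness.

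**Option (a), the default, because the sample size uses only this day.** Day-1 28-region ECS is primary. Day 2 and then day 3 are tested in fixed sequence, each at 0.05 and only if the preceding day is significant. Cost: no confirmatory claim for day 2 or 3 if day 1 misses, and two-sided day-1 power is only about 0.65 at 17 per group. It does badly if the effect builds up over time.

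**Option (b), closer to the three-day objective.** One Mann-Whitney test on each patient's mean 28-region ECS over days 1–3, with single days secondary. Cost: the result is not tied to one day, power falls if the effect fades, and a rule for a missed scan must be written.

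Both hold the error at 5%. A Bonferroni split (0.05 / 3 per day) would also control it, but is dearer: by normal approximation, two-sided per-day power at 17 per group drops from 0.70 to 0.54, and 29 per group would be needed for 0.80.

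Either option takes two or three sentences and needs no new data or extra patients.

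### Does the unadjusted Mann-Whitney test need to be replaced by one adjusted for pulmonary edema at entry?

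*Combined protocol and SAP*

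**What the plan says.** STUDY OUTCOME defines the main endpoint in these terms: "The primary outcome studied will be the Echo Comet Score (ECS) at days 1, 2, and 3 following delivery in the vitamin C vs. placebo". The arms are to be compared by a named rank test: "Mann Whitney U-test will be used for comparing ECS between the two study groups (vitamin C vs. placebo"). No covariate, stratified analysis or regression model is mentioned.

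INCLUSION CRITERIA admits a woman on a single qualifying feature: "Singleton pregnancy with severe featutes of preeclampsia (any of the following"). One item on that list is "Pulmonary edema"; others concern blood pressure, platelets, liver, kidney and neurological signs. Eligibility is judged early, since women "will be included in the study at hospital admission", whereas study medication begins only after delivery.

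STUDY PROTOCOL describes the allocation as follows: "Randomization will be performed in a 1:1 ratio using a computer generated randomization sequence". It names no stratification factor.

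**The concern.** The Echo Comet Score (ECS) is the plan's measure of extravascular lung water, and pulmonary edema is an excess of lung water. A woman who enters with overt edema would be expected to score higher than one who enters on blood pressure or platelet count alone. Both kinds of patient can sit in the same comparison, and with 17 per arm their split is left to chance.

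A statistician used to adjusting for strong baseline predictors will see two possible losses. A chance imbalance in edema could move the estimate in a given trial, and the variance that edema explains stays in the error term and costs power. If the covariate is recorded anyway and adjustment is nearly free, omitting it looks like an oversight, and the choice could not credibly be made once the data had been seen.

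**Working it through.** **1. Inputs from the documents.** SAMPLE SIZE CALCULATIONS gives a day-1 mean ECS of 13 with SD 7, a 46% decrease ("To discern a decrease of 46% in ECS between the study (vitamin C) and placebo groups"), power 0.80, alpha 0.05 and 17 women per group. The difference is 0.46 × 13 = 5.98 points.

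**2. The plan's own figure.** The normal formula is n = 2 × [7 × (z_alpha + z_power) / 5.98]².
- One-sided 0.05: 2 × [7 × (1.645 + 0.842) / 5.98]² = 16.94, so 17 per group. This matches.
- Two-sided 0.05: 2 × [7 × (1.960 + 0.842) / 5.98]² = 21.5, so 22 per group. With 17, power is 0.70.

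Sidedness is not stated. The rest of this check uses two-sided 0.05, where power is tighter and adjustment has the most to offer.

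**3. Validity.** Under the null hypothesis, random allocation makes the two arms exchangeable whatever the mix of edema. Chance imbalance is already part of the test's null distribution. Simulation at 17 versus 17 (40,000 runs per setting) agrees: type I error is 0.047 to 0.050 with normal data and 0.045 to 0.049 with counts for Mann-Whitney, and 0.048 to 0.052 for the adjusted test.

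**4. What the gain depends on.** A yes/no covariate with share p and ECS shift g explains R² = p(1 − p)g² / 49 of the variance. The documents give neither p nor g. Assumed values:
- p = 5%, g = 5: 0.0475 × 25 / 49 = 0.024
- p = 10%, g = 10: 0.09 × 100 / 49 = 0.18
- p = 20%, g = 10: 0.16 × 100 / 49 = 0.33

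**5. Power.** The adjusted test regresses the rank of ECS on treatment and edema. It reverts to Mann-Whitney if at most one of the 34 women has edema, which has probability (1 − p)^34 + 34p(1 − p)^33. Model A is normal with a constant effect of 5.98; Model B is a rounded gamma count with treated values multiplied by 0.54. The overall control mean and SD are held at 13 and 7. Unadjusted power is 0.64 to 0.66 in A and 0.82 to 0.85 in B. Changes are in percentage points of power.

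| Edema share | Chance of at most 1 in 34 | A: gain, shift +5 to +10 | B: gain, shift +5 to +10 | B like-for-like: shift +5 / +10 | B like-for-like: not prognostic |
|---|---|---|---|---|---|
| 3% | 73% | 0.2 to 1.3 | 0.1 to 0.8 | −0.1 / +0.4 | −0.3 |
| 5% | 49% | 0.3 to 2.6 | 0.3 to 1.5 | −0.2 / +1.2 | −0.6 |
| 10% | 13% | 1.3 to 6.2 | 1.0 to 3.9 | +0.2 / +3.3 | −1.2 |
| 20% | 0.5% | 3.0 to 14.1 | 2.3 to 9.2 | +1.5 / +8.3 | −1.4 |

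The last two columns compare the rank regression with the same rank regression without edema. This matters in Model B: Mann-Whitney carries a conservative continuity correction there (size about 0.046) and the regression does not (about 0.050), so part of the gain in the fourth column does not come from the covariate. Model A is free of this artefact, but it puts 15.8% of treated women below zero and so is a rough model for a count.

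**6. Later days.** RATIONALE says of lung water that "it decreases rapidly in the first four days following delivery", so the shift due to edema may fade. If it falls 10, 7, 5 over days 1 to 3 at a 10% share, with mean and SD held at the day-1 values (an assumption), the gain falls 6.2, 2.9, 1.3 points in A and 3.9, 2.2, 1.0 in B.

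**The case for a change.** The best case for adjustment is that the bet is lopsided. The prognostic link follows from what the ECS measures. Against Mann-Whitney as planned, the simulated loss when edema is irrelevant is 0.2 to 0.7 points (A) or 0 to 0.3 (B), while the gain reaches 14.1 or 9.2 points at the top of the range. Power may be tight, since 17 per group gives about 0.70 two-sided. The price is a few sentences, one recorded item and one degree of freedom.

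Much of this stands. Edema is plausibly prognostic, adjustment would be legitimate if fixed in advance, and under favourable inputs it would help. Three things keep it from showing a fault.

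- The upper figures rest on a corner that nothing in the documents supports: one woman in five with overt edema, each shifted by 10 points, or 33% of all ECS variance. At shares of 3 to 5% the gain is 0.1 to 2.6 points.
- The downside is understated in the count model. Like for like, the loss is 0.3 to 1.4 points, and at a shift of +5 with shares up to 10% the change is −0.2 to +0.2.
- The change is less simple than it looks. The feature established at admission may no longer describe a woman at delivery. A fresh edema status before the first dose needs its own definition and a new assessment around delivery, with dosing due in the half-hour that follows. It would also make rank regression on a possibly very sparse yes/no covariate the main test in 34 women.

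The timeline figure cannot be read here, so a pre-dose lung scan, which might serve as a better covariate, can be neither confirmed nor excluded.

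**Conclusion.** The concern does not hold. The plan names a valid test that suits a B-line count, and an unadjusted randomized comparison is a legitimate choice. Each comparison keeps its error rate with or without edema in the model. What remains is a possible power gain of 0.1 to 14.1 points when edema shifts the score by 5 to 10, against a loss of up to about 1.4 points like for like when it does not. Where the trial falls depends on two quantities absent from the documents. Reasonable statisticians could adjust or decline.

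This rests on 17 women per arm, two-sided 0.05, day-1 mean 13 and SD 7, assumed edema shares of 3 to 20% and assumed shifts of 0 to 10 points. It concerns adjustment for entry edema only. The unstated sidedness of alpha and the use of three primary days without a multiplicity rule (up to 1 − 0.95³ = 14.3% family-wise error if the days were independent) are separate questions that covariate adjustment would not resolve.
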